2.2. Study Objectives

2.2.1. Primary Objective

To evaluate the effect of TERN-501 monotherapy on liver fat content as assessed by MRI-PDFF compared to placebo.

2.2.1.1. Endpoint for the Primary Objective

Relative change from baseline in MRI-PDFF at Week 12 for TERN-501 compared to placebo.

2.2.2. Secondary Objectives

- To evaluate the effect of TERN-501 monotherapy on cT1 relaxation time compared to placebo
- To evaluate the effect of TERN-501+TERN-101 on liver fat content as assessed by MRI-PDFF and on cT1 relaxation time compared to placebo
- To evaluate safety and tolerability of TERN-501 monotherapy and TERN-501+TERN-101

2.2.2.1. Endpoints for the Secondary Objectives

- Change from baseline in cT1 relaxation time at Week 12 for TERN-501 compared to placebo
- Relative change from baseline in MRI-PDFF at Week 12 for TERN-501+TERN-101 compared to placebo
- Change from baseline in cT1 relaxation time at Week 12 for TERN-501+TERN-101 compared to placebo
- Patient incidence of treatment emergent adverse events

Final, Version 2.0, 26JULY2023

CONFIDENTIAL

2.2.3. Exploratory Objectives

- To explore the effect of TERN-501 monotherapy on efficacy and markers of target engagement compared to placebo
- To explore the effect of TERN-501+TERN-101 on efficacy and markers of target engagement, compared to placebo and/or each monotherapy
- To evaluate the pharmacokinetics of TERN-501 and TERN-101 administered alone and in combination

2.2.3.1. Endpoints for the Exploratory Objectives

- Change from baseline in the following parameters, as applicable:
 - o ALT, AST, and GGT
 - o FIB-4, CK-18 (M30 and M65), ELF (PIIINP, TIMP-1, HA), PRO-C3, and FAST score
 - TE and CAP
 - o MRI-PDFF (relative change) and cT1
 - o SHBG
 - o Lipid panel (for PD as well as safety evaluation)
 - o rT3
 - o FGF19, bile acids, and 7α C4
- Proportion of responders on MRI-PDFF and/or cT1 with the following:
 - \circ ≥ 30% relative reduction in MRI-PDFF
 - \circ ≥ 80 msec reduction in cT1
- PK parameters (e.g., AUC, C_{max}, C_{tau})

3.1. General Principles

All data processing, summarization and analyses will be performed using Labcorp Drug Development's SAS Environment / Version 9.4 (or later) of the SAS® statistical software package.

Individual patient data obtained from electronic case report forms (eCRFs), central laboratories, external sources, and any derived data will be presented in data listings by patient. The primary data source will be used for all analyses. All data listings that contain an evaluation date will contain a relative study day. Pre-treatment and on-treatment study days are numbered relative to the day of the first dose of study drug which is designated as Day 1. The preceding day is Day -1, the day before that is Day -2, etc.

All outputs will be incorporated into Microsoft Word rich text format (.rtf) files, sorted and labeled according to the International Council for Harmonization (ICH) E3 guideline, E3 Structure and Content of Clinical Study Reports, and formatted to the appropriate page size(s), font type, and font size according to Food and Drug Administration (FDA) guidance of Portable Document Format Specifications.

For categorical variables, summary tabulations of the number and percentage of patients within each category of the parameter will be presented. Percentage calculations will be based on non-missing data, unless otherwise specified. For each parameter, the total number of patients with a response will be provided. Percentages are rounded to 1 decimal place, unless otherwise specified.

For frequency counts of categorical variables, categories whose counts are zero will be displayed for the sake of completeness. For example, if none of the patients discontinue due to "Lost to Follow-up," this reason will be included in the table with a count of 0. Percentages will be presented to 1 decimal place, with the exception of 0, which will be presented without percent, and 100, which will be presented without decimal places. Values less than 0.1% will be presented as "<0.1%." Values less than 100% but greater than 99.9% will be presented as ">99.9%."

For continuous variables, the number of patients, mean, standard deviation (SD), median, 25th (Q1) and 75th (Q3) percentiles, minimum, and maximum values will be presented. The precision of summary statistics, unless otherwise specified will be as follows: mean, median, Q1, and Q3 to 1 more decimal place than the raw data, SD to 2 decimal places more than the raw data, and minimum and maximum to the same decimal places as the raw data. In general, the number of decimal places should not exceed 3 decimal places unless appropriate.

CONFIDENTIAL

For log-normal data (e.g., the PK parameters of area under the concentration-time curve [AUC] and maximum observed concentration [C_{max}]), the geometric mean and geometric coefficient of variation (CV%) will also be presented. The precision of descriptive statistics will be as follows: mean, median, Q1, and Q3 to 1 more decimal place than the raw data, SD to 2 decimal places more than the raw data, the minimum and maximum to the same number of decimal places as the raw data, geometric mean to 3 significant figures, and geometric CV% to 1 decimal place. The PK parameters will be presented to 1 decimal place.

Confidence intervals (CIs) will be provided and will be rounded to 1 decimal place, unless otherwise specified, in the table and listing shell. A full set of summary statistics will only be presented if there are 3 or more values available. If there are less than 3 values, only the min, max, and N will be presented. The other summary statistics will be denoted as not calculated (NC).

For tables where rounding is required, rounding will be done to the nearest round-off unit. For example, when rounding to the nearest integer, values $\ge XX.5$ will be rounded up to XX+1 (e.g., 97.5 will round up to 98), while values $\le XX.5$ will be rounded down to XX (e.g., 97.4 will round down to 97).

All statistical tests comparing groups will be conducted at the 2-sided, 0.05 level of significance, unless otherwise specified. Summary statistics for each treatment group will be presented, as well as the two-sided 95% CIs for comparing groups.

Specifications for table, figures, and data listing formats can be found in the TFL shells specifications for this study.

All data recorded on the case report form will be included in data listings.

3.2. Computing Environments

All descriptive statistical analyses will be performed using SAS software Version 9.4 or higher, unless otherwise noted.

Plasma PK and PD parameters for TERN-501 and TERN-101 will be estimated using non-compartmental methods with Phoenix WinNonlin® Version 8.3 or higher.

Medical history and AEs will be coded using Medical Dictionary for Regulatory Activities (MedDRA) version 23.0. Concomitant medications will be coded using World Health Organization Drug Dictionary (WHODD), B2 Enhanced March 2020.

Study Data Tabulation Model (SDTM) and Analysis Data Model (ADaM) datasets will be prepared using Clinical Data Interchange Standards Consortium (CDISC) SDTM Implementation Guide (IG) Version 3.3, ADaM Version 2.1, and CDISC ADaM IG Version 1.2 including most current occurrence and time to event IGs.

CONFIDENTIAL

3.3. Partial Dates

Imputation of partial adverse event and concomitant medication dates are specified in Appendix 2.

All clinical data recorded on the case report form will be included in data listings.

3.4. Missing Data

Treatment end date will be the date of last dose from the End of Study Treatment page of the CRF. If this is missing, then the last date (dispensing or return) from the study drug accountability page will be used.

3.5. Data Conventions

The precision of original measurements will be maintained in summaries, when possible.

Quantitative safety laboratory tests containing less than (<) and greater than (>) symbols are test results that are below and above quantifiable limits, respectively. In order to retain these values for analysis purpose, the following will be imputed and stored within the analysis datasets:

- For values with \leq , the imputed value will be the numeric portion \times 0.9.
- For values with \geq , the imputed value will be the numeric portion \times 1.1.

PK and PD imputation of values below the limitation of quantitation (BLQ) are specified in Section 7.17.4 and Section 7.18, respectively.

Variables with a non-normal distribution that impacts the interpretation or validity of the planned analysis may have a data transformation applied (e.g., ln, log10).

3.6. Standard Calculations

Variables requiring calculation will be derived using the following formulas:

• Days – A duration expressed in days between one date (date1) and another later date (date2) will be calculated using the following formulas:

```
duration in days = date2 - date1 + 1, where date1 \ge first administration date duration in days = date2 - date1, where date1 < first administration date
```

- Months A duration expressed in months is calculated as the number of days divided by 30.4375
- Years A duration expressed in years between one date (date1) and another date (date2) is calculated using the following formulas:

CONFIDENTIAL

CONFIDENTIAL Protocol Reference: TERNCB-2002

duration in years = (date2 - date1 + 1)/365.25, where date1 \geq first administration date

duration in years = (date2 - date1)/365.25, where date1 < first administration date

• Body Mass Index (BMI) – BMI is calculated using height (cm) and weight (kg) using the following formula:

BMI
$$(kg/m^2)$$
 = body weight $(kg) / ([height (cm)/100]^2)$

• Change (CHG) will be calculated as:

Change = later value – earlier baseline value

• Relative change (PCHG or percent change) will be calculated as:

Relative change = ([Change] / baseline value)
$$\times$$
 100

If a baseline value is 0, the relative change will be missing and not included in summary calculations. Within listings, this value will be displayed as NC (not calculable).

3.7. Treatments

Table 3 presents how the dose groups will be presented in TFLs as treatment groups, including the order.

Table 3 Treatment Group Labels and Ordering

Treatment Group Label	Order on TFLs
Placebo	1
101 10 mg	2
501 1 mg	3
501 3 mg	4
501 6 mg	5
501 3 mg + 101 10 mg	6
501 6 mg + 101 10 mg	7

Screen failures will be presented on by-patient listings where data is available.

3.8. Visits

3.8.1. Windows

In data listings, the relative study day of all dates from first dose will be presented.

Scheduled visit assessments will be determined based on a two-step process using the parameters of exposure to study drug and scheduled visit assessment windows.

Step 1:

• The last dose date (maximum from dates of discontinuation form and exposure data) must be within 14 days, inclusive, of the last assessment of those within the treatment exposure period (12 weeks). If the last dose date is after or within 14 days inclusive of the Week 12 assessment there will be an assumption that all previous assessments were performed while under proper drug exposure. Any assessments performed greater than 14 days of the last dose date will be considered unscheduled irrespective of Table 4 mapping.

Step 2:

- Use Table 4 to initially map the appropriate assessment under consideration
- For multiple assessments mapped to the same scheduled visit interval, select the assessment date that is closest to the target day of the visit window in terms of absolute difference, irrespective of scheduled or unscheduled visit type. Any assessment not selected in the window is considered unscheduled.

In the event of a scheduled visit assessment tie AND the assessment was performed as an original scheduled assessment select this over an unscheduled; if both assessments are unscheduled or scheduled select the first assessment, then classify the other as unscheduled.

Final, Version 2.0, 26JULY2023

CONFIDENTIAL

Labcorp Drug Development Study: 000000231152 Protocol Reference: TERNCB-2002

Table 4 Treatment Period Visit Windows

Target Scheduled Visit	t Scheduled Visit Target Study Day ^a Analysis Window Study Day ^a		
	•	Low	High
Targeted physical examina	ation, vital signs, EC	CG, chemistry and hema	atology labs
Baseline	1	See Section 3.6.2	
Week 2	15	2	22
Week 4	29	23	36
Week 6	43	37	50
Week 8	57	51	70
Week 12	85	71	99
Thyroid axis testing	•		·
Baseline	1	See Section 3.6.2	
Week 2	15	2	29
Week 6	43	37	50
Week 12	85	71	99
Weight, MRI-PDFF, MRI	-cT1, and fibrosis b	iomarkers	·
Baseline	1	See Section 3.6.2	
Week 6	43	29	57
Week 12 ^b	85	71	99
Week 16	For all		
	parameters, use nominal visit as		
	recorded on CRF.		

a Study Day will be calculated from first dose of study drug. Visit windows defined by the low and high values are inclusive.

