Patients who are randomized but do not receive study drug for any reason may be replaced. In addition, patients who discontinue treatment early for reasons other than safety (i.e., withdrawal of consent, lost to follow-up, patient relocated, etc.) may also be replaced, at the Sponsor's discretion. Replacement patients will receive the same treatment assignment as the patient that discontinued treatment early.

Study Centers Planned:

Approximately 40 centers in the United States

Intervention Groups and Duration:

The total study duration will be approximately 22 weeks, consisting of up to a 6-week Screening period (42 days), a 12-week Treatment period, and a 4-week Follow-up period.

Screening Period

The \leq 6-week Screening period initiates upon signing an Informed Consent, at which point eligibility criteria will be reviewed. Each eligible patient will be scheduled for Week 0/Day 1.

Treatment Period

The 12-week double-blind, randomized treatment period will initiate at Week 0/Day 1 after confirming eligibility. The blinded study drugs (TERN-501, TERN-101, TERN-501+TERN-101, or matching placebo) will be orally administered once daily.

Patients will return to the site at Weeks 2, 4, 6, 8, and 12 for safety and laboratory assessments. Study drug will be dispensed at Week 0/Day 1, Week 4, and Week 8. Week 12 is the last day of treatment.

Intensive PK/PD sampling will be performed in approximately 42 patients participating in the PK/PD sub-study on the day of first dose (Week 0/Day 1) and on the day of last dose of study drug (Week 12).

Transient elastography (TE) and controlled attenuation parameter (CAP) by FibroScan[®] will be completed at Screening or Day 1, and Week 12. MRI-PDFF, and cT1 will be completed at Screening, Week 6, and Week 12. FibroScan[®] and MRI-PDFF will be performed at early termination (ET) only if not done within the prior 4 weeks, and the patient has had at least 4 weeks of dosing.

[figure not shown]
All visits through Week 12 will have $a \pm 3$ days visit window from the specific study day.

Follow-up Period

All patients will return to site for follow up safety assessments at Week 16. Week 16 will have a -7 days /+2 days visit window.

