7.12. Fibrosis-4 (FIB-4) Score

The Fibrosis-4 (FIB-4) score helps to estimate the amount of scarring in the liver. The FIB-4 score is calculated as:

[Age (years)
$$\times$$
 AST (U/L)] \div [Platelet Count (10⁹/L) \times ALT (U/L)0.5].

Age at informed consent will be used. Lab values at each visit, from the same visit, will be used. The central lab calculation of FIB-4 will be used in analyses. The FIB-4 score will be calculated at baseline, Week 6, Week 12, and Week 16.

The change from baseline in FIB-4 score will be analyzed in the same manner as specified in Section 7.7 and pairwise comparisons in Section 7.6 using the efficacy analysis set.

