8.3.2. Thyroid Axis Testing

TSH, free T3, free T4, total T3, total T4, and TBG will be collected at Baseline and Weeks 2, 6, 12, and 16, and/or ET. Estimates of the LS mean difference for the pairwise comparisons detailed in Section 7.7 with the associated standard error of the difference, and 95% CI of the difference, the standard error of the difference, and 95% CI of the difference will be presented. Summary statistics will be provided for the levels at each visit and for change from baseline by treatment groups.

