8.3.4. Bone Turnover Markers

The bone turnover markers sCTX and sPINP will be collected at Baseline, Week12, and Week 16. Summary statistics will be provided for each parameter at each visit and for change from baseline at each visit.

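### The 14-day rule in SAP 3.8.1 Step 1, read literally, makes every in-window Week 16 assessment unscheduled and contradicts the SAP's own Week 16 row and planned Week 16 results

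*SAP*

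**What the plan says.** SAP 3.8.1 assigns assessments to visits in two steps. Step 1 is a drug-exposure check. Its opening sentence ties the last dose date to assessments made during the 12-week exposure period, and its second sentence deals with exposure up to Week 12. Its third and last sentence carries no such limit: "Any assessments performed greater than 14 days of the last dose date will be considered unscheduled irrespective of Table 4 mapping".

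Step 2 maps assessments with Table 4. That table is headed as covering the treatment period but also has a Week 16 row. The row gives no day window; it says that for all "parameters, use nominal visit as" recorded on the CRF.

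The SAP then plans results at Week 16:

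- SAP 7.12: "The FIB-4 score will be calculated at baseline, Week 6, Week 12, and Week 16".
- SAP 7.14 and 7.14.1.1: the NAFLD fibrosis score and APRI are also calculated at Week 16.
- SAP 8.3.2: "TSH, free T3, free T4, total T3, total T4, and TBG will be collected at Baseline and Weeks 2, 6, 12, and 16, and/or ET", with summary statistics at each visit.
- SAP 8.3.4: bone markers are collected at Baseline, Week 12 and Week 16. "Summary statistics will be provided for each parameter at each visit and for change from baseline at each visit".

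Safety laboratory results (SAP 8.3), vital signs (8.4) and ECG (8.5) are also summarised visit by visit.

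On timing, Protocol 1.1 states that "Week 12 is the last day of treatment" and that "Week 16 will have a -7 days /+2 days visit window".

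**The concern.** Week 16 is an off-drug visit by design, about four weeks after the last dose. A rule that relabels anything beyond 14 days from the last dose, and that expressly overrides Table 4, therefore catches the whole visit. Nothing in the SAP says whether Step 1 or the Week 16 row prevails.

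What is at stake is the Week 16 column of the by-visit summaries. For completers it is the only scheduled off-treatment visit. For bone markers it is one of only two scheduled post-baseline visits. A programmer who follows the sentence exactly could leave that column empty. One who ignores it would be departing from the signed SAP without a documented reason.

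**Working it through.** **Inputs**

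- Week 12: Day 85 ± 3 (Protocol 1.1 and 1.3), so Day 82 to 88. Last dose for a completer is taken at this visit.
- Week 16: Day 113, −7/+2 (Protocol 1.1 and 1.3), so Day 106 to 115.
- Follow-up after early termination: 4 weeks after last dose, −7/+2 days (Protocol 1.3).
- Patients who stop study drug permanently should stay for the remaining visits through Follow-Up (Protocol 7.1.2).
- Cut-off: more than 14 days from last dose (SAP 3.8.1 Step 1).

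**The plan's own figure.** Nominal gap = 113 − 85 = 28 days, which matches the stated four weeks.

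**Gap from last dose to follow-up**

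| Patient | Shortest | Longest |
|---|---|---|
| On-schedule completer | 106 − 88 = 18 | 115 − 82 = 33 |
| Early termination | 28 − 7 = 21 | 28 + 2 = 30 |
| Last dose Day 57, stays to Week 16 | 106 − 57 = 49 | 115 − 57 = 58 |
| Last dose Day 29, stays to Week 16 | 106 − 29 = 77 | 115 − 29 = 86 |

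Using the SAP 3.6 day-count convention, which adds 1, the completer range becomes 19 to 34 days. The conclusion does not change.

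**Could an in-window Week 16 visit pass the rule?** The last dose would have to fall on Day 106 − 14 = 92 or later. The Week 12 window closes on Day 88, so no on-schedule patient can meet it.

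**Does being unscheduled mean being left out of by-visit tables?** No sentence says so outright. Three places point that way:

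- SAP 3.8.1 presents the two steps as the way scheduled visit assessments are determined, and Step 2 gives the unscheduled label to duplicates not chosen for a visit.
- SAP 7.7 calls for reporting of all scheduled visits.
- Protocol 9.4.5 summarises vital signs and safety laboratory values by scheduled time point.

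The exclusion is therefore a reasonable inference, not a stated rule.

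**What does not depend on the visit label**

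- Treatment-emergent laboratory abnormalities, defined through Week 16 (SAP 8.3.1).
- Treatment-emergent adverse events, counted through 30 days after last dose or the Follow-Up Period (SAP 8.2).
- Worst post-baseline QTcF categories (SAP 8.5).
- By-patient listings.
- The primary and secondary MRI endpoints, which are at Week 12.

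**The case against.** The best reply is that Step 1 should be read as a whole. Its first two sentences concern the 12-week exposure period, Table 4 is headed as a treatment-period table, and the rule's evident purpose is to stop off-drug values being labelled as on-treatment visits. That purpose has no application to a visit that is off drug by design. Week 16 has its own nominal-visit rule with no day window, so the override can be read as reaching only the day-window mapping. Five later sections name Week 16, and a programmer who produced empty columns would contradict all of them.

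Most of this stands. It shows that the SAP intends to report Week 16, and it rules out treating the loss of those results as settled. It does not remove the conflict: the last sentence speaks of any assessment, overrides a table that contains the Week 16 row, and exempts nothing.

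A reader might also infer that the plan gives up a prespecified test of whether thyroid or bone effects reverse off drug. The documents do not support that. No objective or endpoint names reversibility, and the protocol describes Week 16 only as a follow-up safety visit.

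**Conclusion.** The point holds as an internal contradiction of low severity. Followed to the letter, the last sentence of Step 1 reclassifies every in-window Week 16 assessment in all seven arms, because every such visit is at least 18 days after last dose against a limit of 14. That conflicts with the Week 16 row of Table 4 and with five sections that plan Week 16 results.

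It would go too far to say that Week 16 results will drop out of the tables. That outcome needs two things: literal programming of one sentence against the SAP's evident intent, and the inference that unscheduled records are left out of by-visit summaries. Nor is 18 to 33 days the range for everyone; it applies to completers on schedule, and patients who stop drug early but stay in the study have longer gaps.

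The arithmetic assumes that visits are held within their windows and that a completer's last dose is taken at the Week 12 visit.

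**What to change.** In SAP 3.8.1, limit the last sentence of Step 1 to assessments that Table 4 maps to Weeks 2 to 12. Add that the nominal Week 16/Follow-Up visit is exempt from the 14-day rule and is summarised as Week 16. The treatment of late assessments at Weeks 2 to 12 stays as it is.

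The cost is one sentence in the SAP and a check of the visit-mapping code. No new data and no protocol amendment are needed.

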Coagulation ^c	х	х								Specific analytes are listed in Appendix 1. PT/INR will be tested at Screening, Week 0, and if significant abnormal liver function is observed.	
Urinalysis ^c	х				Х			х	х	Specific analytes are listed in Appendix 1. Microscopic examination is required if blood or protein is abnormal.	
Urine Drug Screen ^c	Х	Х		Х		Х	Х	Х	x	Randomization may proceed at Week 0 provided exclusion criteria 29 and 30 are not met.	

	Screening		1	Freatmen	t Period ^f			Follow -Up ^b ET ^a		Notes	
Visit	Screening	Week 0	Week 2	Week 4	Week 6	Week 8	Week 12	Week 16			
Study Day		Day 1	15	29	43	57	85	113			
Schedule Window (days)	-42 days		± 3	± 3	± 3	± 3	± 3	-7 /+2		Patients discontinuing the study at any time for any reason (Early Termination) should complete the ET visit as soon as feasible and return for a Follow-Up visit 4 weeks (-7 days /+2 days) after the last dose of study drug.	
Thyroid Axis Testing ^c	х	х	х		х		х	х	х	All thyroid axis samples (including any repeat tests) should be collected in the morning at approximately the same time on each visit day. Specific analytes are listed in Appendix 1. Post-dose T4 and rT3 results will remain blinded as outlined in Section 8.1.9.1. Refer to Section 8.1.8 for additional detail on thyroid axis safety monitoring. TBG and rT3 will be analyzed only at Week 0/Day 1 and Week 12 or ET.	
Bone turnover markers ^c		Х					х	х	х	Includes sCTX and sPINP.	
Sex Hormone Panel ^c		Х					X	Х	х	Specific analytes are listed in Appendix 1.	
Serology	х									Includes HBsAg, anti-HCV and anti-HIV.	
COVID-19 Assessment ^{c,g}	х	Х			х		х			Screening and on study COVID-19 assessments should be conducted in accordance with Appendix 9.	
Serum pregnancy test ^c	Х	Х		х		х	х		х	WOCBP only.	
Urine pregnancy test ^c		х								WOCBP only. Urine pregnancy test will be completed on Day 1 and negative test result must be confirmed prior to randomization.	
Serum FSH	х									Women of non-childbearing potential only. In the absence of 12 months of amenorrhea, confirmation with more than one FSH measurement is required.	
Blood Alcohol Test	Х										

	Screening]	Freatmen	t Period ^f			Follow -Up ^b	ET ^a	Notes
Visit	Screening	Week 0	Week 2	Week 4	Week 6	Week 8	Week 12	Week 16		
Study Day		Day 1	15	29	43	57	85	113		

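### SAP Table 4 leaves Days 30-36 and 51-70 outside every thyroid visit window, so early-termination and repeat thyroid panels on those days enter no by-visit summary

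*SAP*

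**What the plan says.** SAP 3.8.1 maps assessments in two steps. Step 1 requires the assessment to lie within 14 days of the last dose. Step 2 says "Use Table 4 to initially map the appropriate assessment under consideration", then keeps the value closest to the target day in each window. On the rest it says "Any assessment not selected in the window is considered unscheduled".

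Table 4 has a block headed "Thyroid axis testing" with three post-baseline rows: Week 2 (target Day 15, Days 2-29), Week 6 (target Day 43, Days 37-50) and Week 12, which reads "Week 12 85 71 99". The footnote says "Visit windows defined by the low and high values are inclusive". Week 16 uses the nominal visit. There is no ET row.

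SAP 8.3.2 says that the thyroid tests "will be collected at Baseline and Weeks 2, 6, 12, and 16, and/or ET". It then plans: "Summary statistics will be provided for the levels at each visit and for change from baseline by treatment groups". It also plans least-squares mean differences by reference to SAP 7.7. It gives no rule for displaying an ET panel or a panel that falls outside every window.

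For two analytes of the thyroid panel the Protocol's Schedule of Activities is narrower: "TBG and rT3 will be analyzed only at Week 0/Day 1 and Week 12 or ET". SAP 7.11 analyses rT3 and the FT3/rT3 ratio as efficacy variables.

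**The concern.** The chemistry block of Table 4 runs without a break from Day 2 to Day 99 because it has Week 4 (Days 23-36) and Week 8 (Days 51-70) rows. The thyroid block keeps the chemistry bounds for Weeks 6 and 12 but has neither of those rows. A patient who leaves the study on, say, Day 33 or Day 60 has chemistry assigned to a visit, while the thyroid panel from the same ET visit is assigned to none.

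The trial drug is a thyroid-receptor agonist. Under Protocol 7.1.2 a confirmed, clinically significant TSH abnormality is a reason to stop study drug, so which panels go missing from the summaries may be related to the result itself. Nothing else in the thyroid plan clearly picks these values up by visit. The shift tables in SAP 8.3.5 name hematology, chemistry and urinalysis. The End of Treatment fallback in SAP 3.8.3 is used for the MRI-PDFF carry-forward analysis and is not called for in 8.3.2.

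**Working it through.** **1. Inputs (SAP Table 4, inclusive bounds)**

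| Visit | Target day | Chemistry window | Thyroid window |
|---|---|---|---|
| Week 2 | 15 | 2-22 | 2-29 |
| Week 4 | 29 | 23-36 | none |
| Week 6 | 43 | 37-50 | 37-50 |
| Week 8 | 57 | 51-70 | none |
| Week 12 | 85 | 71-99 | 71-99 |

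**2. Coverage of Days 2-99 (98 days)**

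- Chemistry: 21 + 14 + 14 + 20 + 29 = 98 days; none uncovered.
- Thyroid: 28 + 14 + 29 = 71 days; 98 - 71 = 27 uncovered.
- The uncovered days are 30-36 (7 days) and 51-70 (20 days). 27/98 = 27.6%.

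**3. How the bounds arise**

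- Chemistry midpoints between targets: (15+29)/2 = 22, (29+43)/2 = 36, (43+57)/2 = 50, (57+85)/2 = 71. These reproduce the chemistry bounds, with Day 71 given to Week 12.
- Thyroid midpoints: (15+43)/2 = 29 and (43+85)/2 = 64. Only the Week 2 upper bound (29) follows the thyroid schedule. The Week 6 bounds (37, 50) and the Week 12 lower bound (71) do not.
- The weight and MRI block also goes from Week 6 to Week 12, and it uses Days 29-57 for Week 6. Under either convention seen in the table (midpoints or about ±14 days), Days 30-36 and 51-57 would belong to Week 6.

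**4. Which panels are affected**

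The Protocol's visit window is ±3 days, giving Days 12-18, 40-46 and 82-88. All lie inside a thyroid window. What can fall in a gap is an ET panel, a repeat after an abnormal result (Protocol 8.1.8) or a visit well off schedule.

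**5. Size, under stated assumptions**

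The documents give no dropout rate. Assume that 10-15% of 140 leave early (14 to 21 patients), uniformly over Days 2-85 (84 days), each with an ET panel within 14 days of the last dose.

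- ET panels on unmapped days: 27/84 = 0.321; 0.321 × 14 = 4.5 and 0.321 × 21 = 6.8, so about 4-7.
- TSH, T3 and T4: suppose the gaps were closed at the midpoints (Week 6 = 30-64, Week 12 = 65-99) and the patient's earlier panels were on target. On Days 30-36 the ET panel would be the Week 6 value, and on Days 65-70 the Week 12 value. On Days 51-64 the Day 43 panel is closer to target, so the ET panel would still not be selected. The gap itself decides the outcome on 7 + 6 = 13 of the 27 days: 13/84 × 14 = 2.2 and 13/84 × 21 = 3.3, so about 2-3 panels.
- Week 12 pairwise comparisons (SAP 7.7): only Days 65-70 would newly enter. 6/84 × 14 = 1.0 and 6/84 × 21 = 1.5 patients in the whole trial.
- rT3 and TBG: under the Schedule of Activities no Week 6 value exists to compete, so an ET value on any of the 27 days can be the patient's only post-baseline value. The 4-7 range applies here.

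**The case against.** The strongest reply is that gaps in Table 4 may be deliberate. The weight and MRI block has gaps too (Days 2-28 and 58-70), and Week 12 is Days 71-99, that is Day 85 ± 14, in all three blocks. Bounded windows keep a value labelled Week 12 close to Week 12. This stands in part. A reader might infer from the Week 2 bound of 29 that contiguous thyroid windows were intended and that the whole block was copied from chemistry. The documents do not show the intention, and the Week 2 row differs from chemistry. What remains is narrower: a Week 6 window of Days 37-50 that matches neighbours the thyroid schedule does not have.

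A second reply is that no safety information is lost. This also stands. SAP 8.3 lists all safety laboratory data by patient, Protocol 8.1.8 requires abnormal thyroid results to be repeated and followed, and signs or symptoms of thyroid dysfunction are recorded as adverse events and summarised without Table 4. The effect is confined to the by-visit summaries and change from baseline.

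Third, a reader might infer that the lost panels are mainly those of early leavers and that 4-7 TSH, T3 and T4 values disappear. There is no count behind the first, since repeat tests can also fall in the gaps. The second ignores the closest-to-target rule. The range is also generous: patients who only stop drug are to stay in the study, and those lost to follow-up may give no ET panel.

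Finally, wider windows have a price: a Day 65 panel would be labelled Week 12, 20 days before target. That is fair, and it is why an ET row matters as much as the window change.

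**Conclusion.** The point holds as a minor correction. Applied as written, Table 4 gives thyroid panels on Days 30-36 and 51-70 no analysis visit, and SAP 8.3.2 supplies no other row for them although it names ET as a collection point. The day ranges follow exactly from the table. The patient counts are illustrative: about 4-7 ET panels on unmapped days, of which about 2-3 would otherwise have been the selected TSH, T3 or T4 value, given the assumed 10-15% early exit, uniform timing and complete ET sampling. The consequence is clearest for rT3 and TBG, where an ET value may be the only one after baseline. Safety summaries and exploratory analyses are affected; the primary MRI-PDFF analysis is not.

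**What to change.** Two changes are needed, because neither does the whole job alone.

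1. In SAP Table 4, close the thyroid gaps, for example Week 2 = Days 2-29 (unchanged), Week 6 = Days 30-64 and Week 12 = Days 65-99. Keep the closest-to-target rule.
2. Add an ET or last-on-treatment row to the thyroid summaries in SAP 8.3.2 and to the rT3 analysis in SAP 7.11, and state how soon after the last dose a panel may be drawn to count. This recovers Days 51-64 for TSH, T3 and T4. It also gives rT3 and TBG a proper place: with wider windows alone, an early leaver's value could sit under Week 6, where the Schedule of Activities plans no such measurement.

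The cost is three numbers in one table and one added row in two sets of outputs. No new data are needed. The downside is that a few values will sit further from their target day; showing the study day in the listings, as already planned, makes that visible.
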